6.2 Subjects and Inclusion/Exclusion Criteria

Patients with non-traumatic ICH admitted to the United Hospital Neurological Intensive Care Unit (Neuro-ICU). The 2016 ICD-10-CM diagnosis code for ICH is 161.9 Non-traumatic ICH generally results from the rupture of blood vessels in the brain, causing blood to collect, form a clot and cause pressure to surrounding tissue. This is most commonly due to hypertension, blood vessel malformation(s), and/or dysfunctional protein(s) leading to weak vessels. The presenting behavior is quite similar with symptoms such as headache, nausea, vomiting, sudden weakness or numbness of the face, arm or leg, temporary loss of vision, seizures, and/or loss of consciousness. Approximately 2/3rds of all ICH's have a volume greater than 20cc.

6.2.1 Major Inclusion Criteria

1. Age ≥ 18 years old and < 80 years.
2. Diagnosis of primary ICH ≥ 20 cc in volume.
3. Enrollment within 48 hours from initial symptoms.
4. Signed informed consent from the patient or obtained via their legally authorized representative (if the patient is not able to sign the informed consent themselves). The patient's decisional capacity to either provide or refuse consent will be determined using the Glasgow Coma Scale (GCS), which is being assessed at baseline and at 24 hours (+/- 6hrs) after enrollment. A potential study participant with a GCS > 14 will be asked to

provide their own initial study consent. A GCS \leq 14 would indicate the need to pursue consent via legally authorized representative. Patient and/or LAR must be English speaking.

6.2.2 Major Exclusion Criteria

1. Current need for renal replacement therapy (RRT).
2. GFR of <30 mL/minute at time of admission.
3. Participation in another study for ICH or intraventricular hemorrhage.
4. ICH related to infection, thrombolysis, subarachnoid hemorrhage, trauma or tumor.
5. Presence of HIV or active fungal infection that is known based on information in the EMR.
6. Continued use of digoxin or amlodipine (as recommended by the manufacturer due to CYP3A inhibition).
7. Active hepatic failure as defined by AST >160 units/L and/or ALT >180 units/L, or total bilirubin levels greater than four times normal levels (>4.8 mg/dL).
8. Serum $\text{Na}^+ \geq 145$ mmol/L (admission labs or any time prior to recruitment/enrollment).
9. Unable to receive conivaptan based on contraindications indicated by the manufacturer.
10. Pregnant or lactating females.
11. Not expected to survive within 48 hours of admission, or a presumed diagnosis of brain death.

6.3 Subject Recruitment

The PI, co-investigators and study team members, will screen and recruit participants from the non-traumatic ICH patient population admitted to the United Hospital Neuro-ICU meeting the study inclusion and exclusion criteria. Investigators will only screen patients seen as part of their normal clinical practice in the Neuro-ICU. Other physicians in Neurology and the Neuro-ICU will be informed of the study by an informational letter sent by the PI, and/or during departmental meetings where the PI will discuss the study. An informational letter, list of inclusion and exclusion criteria and a study binder will also be housed in the Neuro-ICU for reference.

6.4 Sample Size

This study is looking to preliminarily evaluate the safety, tolerability, and efficacy (presence of moderate reduction in CE), and as a ratio of ICH volume to CE volume. Unfortunately, it is not powered to provide robust statistical evaluation of safety and tolerability, nor to detect differences in efficacy, due to time and budgetary limitations.

Seven (7) patients will be treated with conivaptan (40mg/day; four 20mg doses over a 2 day period) in addition to conventional medical means. This number of patients takes into account information in the conivaptan in TBI patients study by Galton et al (2011), use of glyburide in ICH by Sheth et al. (2014), as well as time and budgetary limitations.

The goal is to enroll all seven (7) patients within an 18-month period. This recruitment goal should be achievable since:

- 1) according to the PI's experience, (based on 2015 data) ~50-70 ICH patients (ICD-10-CM code 161.9) are admitted per year to United Hospital and
- 2) according to a recent electronic feasibility search, in the year 2015, 55 patients with a diagnosis of ICH were admitted to United Hospital. Of these patients, the PI determined that 9 would have been eligible for the study, based on the study's inclusion and exclusion criteria.

If a patient decides to withdraw for any reason during the study duration or the LAR wants to withdraw a patient for any reason during the study duration, the patient's data collected up to point of withdrawal

will remain in the database and will be analyzed. If the patient/LAR is against any of the data being used, we will grant this request.

The PI may withdraw the subject from the study without patient/LAR consent if considered appropriate. The reason to withdraw would include complications related to the use of conivaptan. For safety, if withdrawn from the study, it would be in the best interest of the patient to allow follow-up outside the study.

The consent will explicitly detail all aspects of the study (the purpose, methods, benefits, risks).

6.7 Why a patient should participate in this trial?

ICH is a devastating disease representing approximately 15% of all strokes in the United States (Adams 2005, Thomas et al 1996). The 30 day mortality is ~ 40% with only admission to a neuro-ICU and the use of a CT scanner demonstrating improved outcomes (Thomas et al., 1996; Diring & Edwards, 2001). Nearly as great are the costs to society, with the total lifetime cost for annual US cases >\$4B and nearly 35% of years of potential life lost because of stroke (Thomas et al., 1996). This devastation is influenced by the dynamic injury processes involved in ICH. Following the initial hemorrhagic injury, CE develops. This peaks between 7-14 days after the initial bleed ([Venkatasubramanian](#) 2011). Worsening CE has been implicated in delayed neurological deterioration, and worse outcome, through the elevation of ICP (Mayer & Sacco, 1994). Elevations in ICP reduce the ability of blood to reach the brain, exacerbating the injury and producing ischemia. The formation of peri-hematoma edema contributes to an increased volume of ~75% (Gebel et al., 2002). Animal models of ICH demonstrate a large peri-hematoma area that undergoes neuronal death characterized by increased water content and inflammation (Theix & Tsirka, 2007). Reduction of this edema may reduce the degree of neuronal death, potentially improving outcome and decreasing hospital LOS. Further, a shorter time in the neuro-ICU, much of which is focused on management of CE, would mean decreased hospital costs in the form of less nosocomial infections.

Studies in neurocritical care are often limited in their design and scope because many of the common therapies, despite a paucity of clinical evidence, are considered “standard of care.” (Chesnut, 2012). This holds true in the management of CE and ICP, where a wide variability in treatment exists among intensivists (Hays et al., 2010). The two most commonly used agents for the medical management of CE and elevated ICP, mannitol and hypertonic saline, do not demonstrate any evidence of improving clinical outcome (Grande, 2012). Mannitol use is common, but is limited by its deleterious effects on renal function, and fluctuations in intravascular volume and pH. Most concerning is the slow elimination of mannitol from the CSF which may potentially require progressively higher doses, over time, to control ICP, and may result in rebound CE (Nau et al., 1997; McGraw & Howard, 1983). Increasingly, HS is being used to abate CE. However, this therapy has not demonstrated any survival or outcome benefit despite reductions in ICP (Bulger et al., 2010; Strandvik, 2009). The use of hypertonic saline may be associated with increased risk of BSI, and trends to increased risk of nosocomial and urinary tract infections (Bulger et al., 2010). Recently, a retrospective review of patients receiving HS in a single center’s neurocritical care unit demonstrated a correlation between the degree of hypernatremia and hyperchloremia induced by HS and changes in renal function heralding the development of acute kidney injury ([name] et al., 2014). Therefore, any new therapy for CE in ICH should have less or equivalent side effects to mannitol and HS.

It is with this balance in mind, the need for effective therapies in a devastating disease and the continued use of historically approved therapies, that this study is proposed. The welfare of our patients is the primary goal of this trial. Our first goal *Primum non nocere*, to do no harm, is central to this study (Ross, 1988). All patients will receive the standard of care as outlined by the most recent

American Heart Association and Neurocritical Care Society Guidelines for the management of ICH. This will include, but not be limited to, serial clinical and paraclinical evaluations including CT scans, metabolic profile, echocardiography, etc. Current standards-of-practice, including euvolemia targets, electrolyte replacement, venous thrombosis prophylaxis, normoglycemia, etc. will be maintained in this population. The risks most commonly seen with conivaptan use are hypotension (associated with volume loss), site reactions, and electrolyte abnormalities including hypokalemia and hypomagnesemia that may result in dysrhythmia. Thus, patients will be closely monitored for these and other problems. Finally, to evaluate for any unforeseen problems with the use of this medication, these patients will receive standard of care practice, including neuroimaging and outpatient clinic follow-up.

The seven patients in this study will receive 40mg/day of the study medication conivaptan. In this early phase study, our focus will be to assess the safety and tolerability of this medication. The available clinical data on conivaptan in the neurocritical care population suggest the potential harm is negligible. Data in TBI patients demonstrate conivaptan is safe and well tolerated using a single dose (20mg) to increase Na⁺ in a controlled fashion to reduce ICP (Galton et al., 2011). Previous work has demonstrated the safety and tolerability of conivaptan, in doses ranging from 20-80mg/day, in the neurocritical care population (Murphy et al., 2009; Wright et al., 2009; Naidech et al., 2010; Dhar & Murphy-Human, 2011). Conivaptan has been demonstrated to be safe and effective in lowering ICP, and increasing serum sodium, in the neurocritical care population (Murphy NCC '09, Wright NCC '09, Dhar NCC '11, Galton NCC '11). Also noted have been improvements in CPP and stable blood pressure, and a prolonged reduction in ICP. Finally, the method of intermittent bolus dosing of conivaptan is equally effective in raising and maintaining serum sodium in the neurocritical care population as continuous infusion, with potentially less risk of adverse reactions including phlebitis (Murphy NCC '09, Wright NCC '09).

Conivaptan, a non-selective Arginine-Vasopressin (AVP) V_{1A}/V₂ antagonist that reduces aquaporin 4 production and promotes aqueresis, is approved for the treatment of euvolemic and hypervolemic hyponatremia (Cumberland Pharmaceuticals, 2014). The exact cause of the observed reduction in ICP with conivaptan is uncertain. However, the mechanism most likely represents a combination of an acute pure aqueresis, removing free water from brain tissue, and a sustained down regulation of aquaporin 4 to abate/slow development of CE (Dhar NCC '11, Liu X NCC '10, Zandor [Handb Exp Pharmacol](#). 2009). The V₂ antagonism of conivaptan promotes free water loss, and the V₁ antagonism may improve CBF and reduce blood brain barrier permeability (Taya et al., 2008; Trabold et al., 2008; Dhar & Murphy-Human, 2011; Vakili et al., 2005; Kleindienst et al., 2006; Fernandez et al., 2001). Notably, serum sodium tends to correlate inversely with both ICP and CE (Nathan NCC '07). The early use of conivaptan could potentially be used clinically to reduce CE by these means.

It is with this in mind, the research team feels justified in pursuing this study with the hopes that the data obtained will lead to potential good and removal of harm in future patients with this devastating disease. Given the enormous costs of ICH, problems with current therapies, and variability in treatment, there is an urgent need to identify a therapy that has a better safety and effectiveness profile compared to the currently used agents. This study will use a dose (40mg/day) currently approved. Further, given that the primary purpose of the use of this medication in this study is not to correct hyponatremia, an IND from the FDA was sought and determined exempt (FDA IND submission/exemption # 119424).

Our central hypothesis is that through reductions in AQP4 expression, the early use of conivaptan will reduce CE while also being safe to the patient. Our long term goal is to show that early use of conivaptan in ICH will reduce CE. If this reduction is possible, we hypothesize improved outcome and reducing the need for rescue therapies, ICU length of stay, and overall treatment cost will follow. However, more data is needed to evaluate the dosing and amount of drug. With respect to

conivaptan's efficacy in correction of hyponatremia, a direct dose-response relationship exists (Onuoho et al., 2010). Further, this effect was more noted at milder degrees of hyponatremia, suggesting higher doses may be required to achieve a hypernatremic state (Onuoho et al., 2010). This proposed study is an essential first step in understanding the role of conivaptan in CE management. Prior to any mechanistic investigations, a fundamental understanding of dosing and toleration must occur. If this study demonstrates the desired effect, work can take place identifying the optimal dosing and frequency needed for maximal effect. Later studies could ask questions on efficacy. Should such studies prove fruitful, mechanistic investigations using MRI and microdialysis could elucidate effects on membrane integrity, inflammation, and secondary cell injury.

Prior clinical experience suggests patients enrolled in this study will not be harmed. However, patients enrolled may not be helped by participating in this study either; others may be helped by what is learned from this research. Patients initially enrolled, or their LAR, may stop participation at any time. If this happens, they will still be followed-up for safety reasons. Patients will receive the same medical care whether or not they participate in this study. There will be no penalties or loss of benefits if patients choose not to participate. Patients will be told about any significant information that is discovered that could reasonably affect their willingness to continue being in the study. Finally, we do not expect there to be any additional costs to the patients if they participate in this study. Items related to the routine medical care that patients would receive even if they did not participate in this study will be billed to their insurance provider. Finally, there will be no compensation for participation in this study.

6.8 Treatment with Conivaptan

Note: An Investigational New Drug (IND) application for this label use of conivaptan has been submitted to the FDA. After extensive discussions, it was felt this use at this dose did not require an IND (FDA IND submission/exemption # 119424).

Patients will receive 20mg IV of the study drug every 12 hours equaling 40mg/day over 2 days (4 doses total), in addition to the standardized ICH management targets using the PI's version of standardized ICH management targets which are adapted from the 2015 AHA/ASA *Guidelines for the Management of Spontaneous Intracerebral Hemorrhage* and the 2007 Brain Trauma Foundation *Head Injury Guideline*. This will ensure that all the patients will be managed similarly, to decrease the potential for variability commonly seen in "standardized" treatments. Usual standard of care can include sedation and analgesia as needed, elevation of the head of the bed, mannitol and/or saline as needed to reduce ICP, and temperature control with antipyretics such as acetaminophen.

The conivaptan bolus (20mg), which is premixed with 100ml of 5% dextrose in water, is infused (peripherally) over 30 minutes, most commonly through an already placed central line. The conivaptan will be ordered through the hospital's clinical pharmacy. Daily doses greater than the 40mg/day dose being used in this study (i.e., 80mg/day) have been shown to be safe in several studies (Zeltser et al., 2007; Verbalis et al., 2008; Annane et al., 2009; Ghali et al., 2009).

Seven (7) patients will be receiving conivaptan in addition to standardized management.

Electrolytes (obtained from a comprehensive metabolic panel, magnesium, & phosphorus test) will be drawn 6 hours after every conivaptan dose (4 total doses over 2 days). However, these labs may be done sooner (e.g., 2 hours after a conivaptan dose) based on the patient's progress/need and/or the attending physician's direction. The comprehensive metabolic panel will be utilized for these 4 analyses due to its incorporation of several additional parameters (over the basic metabolic panel) needed for the study. The study will cover the costs of this. If the patient's serum Na⁺ becomes ≥ 160

Protocol NSJC-1601 NCT03000283

V6_4APR2018

mmol/L, or increases >12 mmol/L in a 24 hour period, further administration of the study drug will cease. If the patient has not completed the sequence of doses, they will be eligible for the remaining doses if their serum sodium falls below the threshold of 150 mmol/L, or after 24 hours in the case of increases of >12 mmol/L. Need for further use of hypertonic saline or mannitol is left to discretion of the treating physician

All patients will have CT scans at baseline and ~24, 72, and 168 hours (7 days) from enrollment to check for bleeding, lasting edema, or rebound edema. An 8 hour variance is permitted. It is preferable that the CT scans be done at 3mm increments as this is helpful for volume analysis, but 5mm is acceptable. Further imaging is left to the discretion of the treating/primary service physician.

Electrolytes (standard-of-care, basic metabolic panel) for all subjects/patients will be measured every 12 hours for the first 72 hours of the study, and then daily after 72 hours. This is considered a regular schedule based on clinical need. However, during the ~48 hour period when the subjects are receiving conivaptan, a comprehensive metabolic panel, Mg, and PO₄ will be drawn and analyzed 6 hours after each conivaptan dose. These labs may be done sooner based on the patient's progress/need and/or the attending physician's direction.

Neurological exams (e.g., EEGs), vital signs, and urine output measurements will be conducted as per Neuro-ICU protocol.

The need for ancillary monitoring tools (i.e. EVDs, bolts, microdialysis, EEG, near-infrared spectroscopy) will be at the discretion of the treating physicians.

No statin will be initiated within the 1st week following treatment with conivaptan. And, all statin medications will be held from enrollment to day 7 following conivaptan in patients selected for the study. Statins can promote hemorrhage. Those patients who are in-eligible or refuse the study will resume/assume statin use at the treating physician's discretion.

Neuro-ICU personnel/nurses will assist the PI and Co-I with patient care following both standard-of-care and study parameters as part of their normal duties, to maintain the flow of excellent patient care. Therefore, they are not listed on the study budget as study personnel.

Table 1. Project Schema

Assessment	Baseline	Enrollment ^b (within 48 hrs of onset)	6 hours from dose	12 hours from enrollment	6 hours from dose	24 hours from enrollment	6 hours from dose	36 hours from enrollment	6 hours from dose	72 hours from enrollment	Days 3-6	Day 7	Discharge	Follow-up
Inclusion/ exclusion criteria	X ^a													
Consent Process	X ^a													
Patient demographics	X ^a													
Medical history	X ^a													
Clinical Assessment														
GCS	X ^c					X ^c				X ^c		X ^c	X ^c	X ⁱ
APACHE II	X ^c													
mRS	X ^c												X ^c	X ⁱ
ICH	X ^c													
RIFLE	X ^c												X ^c	X ⁱ
Imaging														
CT scan (non- contrast)	X ^d					X ^d				X ^d		X ^d		X ⁱ
Study Drug														
Conivaptan (20mg)		X ^f		X ^f		X ^f		X ^f						
Laboratory Tests														
Comprehensive metabolic Panel	X		X ^e		X ^e		X ^e		X ^e					
Magnesium	X		X ^e		X ^e		X ^e		X ^e					
Phosphorus	X		X ^e		X ^e		X ^e		X ^e					
EMR Data Collection^h														
Vital signs	X		X	X	X	X	X	X	X	X	X	X	X	
ICP monitoring	X		X	X	X	X	X	X	X	X	X	X		
Mannitol monitoring	X		X	X	X	X	X	X	X	X	X	X		
Sodium monitoring	X		X	X	X	X	X	X	X	X	X	X		
Medication log	X					X					X	X		
Cardiac monitoring	X		X	X	X	X	X	X	X	X	X	X		
Intake/Output	X					X				X	X	X		
Adverse event log	X	X	X	X	X	X	X	X	X	X	X	X	X	X ⁱ

^aOccurs prior to enrollment. Other standard-of-care activities that will have occurred (between hospital arrival to 6 hrs post-arrival): 1) CT +/- CTA/CTV, 2) identify and correct coagulopathy, 3) identify and correct blood pressure (BP), 4) identify and correct ICP, and 5) admission to Neuro-ICU.

^bEnrollment needs to occur within 48 hrs from initial symptoms.

^cClinical assessments can be study only or standard-of-care activities with a time window of +/- 6 hours.

^dAdmission and 24-hr stability CT scans are standard-of-care. Additional CT scans, other than the study related 72-hr and 7-day (168 hours) scans, may be done as clinically indicated by treating physician. All scans have a time window of +/- 8 hours.

^eDependent on conivaptan dose. Each needs to be drawn and analyzed 6 hours after each conivaptan dose. However, these labs may be done sooner (e.g., 2 hours after a conivaptan dose) based on the patient's progress/need and/or the attending physician's direction. Otherwise, standard-of-care labs (e.g., BMP) are drawn and analyzed every 12 hrs during the first 72 hrs after admission, followed by daily draws and analyses.

^fDependent on when the 1st of the 4 doses was started.

^hStandard-of-care information collected as part of normal clinical practice will be recorded from the electronic medical record. Information may be recorded on a daily basis or after the protocol is complete.

ⁱFollow-up visits will be conducted as part of normal clinical practice and information recorded, if available, from the electronic medical record. Three month post-discharge follow-up visits are standard-of-care.

Note: Training and informational sessions covering all aspects of the study (e.g., patient enrollment, treatment, ordering of lab tests, data collecting, etc.) will be held prior to the start of the study.

6.9 Primary Assessments (Safety and Tolerability)

Conivaptan was approved by the FDA in 2005 for the treatment of euvolemic and hypervolemic hyponatremia in a hospitalized setting using doses of 20-40mg/day. In the 11 years it has been on the market, numerous studies using it at doses ranging from 20-80mg/day have been done furthering the data on its effect on hyponatremia (National Monograph, 2006; Ghali et al., 2009; Zeltser et al., 2007; Verbalis et al., 2008; Annane et al., 2009; Human et al., 2012; Marik & Rivera, 2013), as well as studies showing its lowering of ICP in patients with TBI (Dhar & Murphy-Human, 2011; Galton et al., 2011). These benefits should relate to a decrease in CE.

In all these studies, conivaptan was well tolerated and safe, with no drug-related serious adverse events observed. For example, in the Ghali et al (2009) study, no deaths were study related, and the side effects of headache, hypotension, nausea, and constipation occurred most frequently. Based on these observations, we expect only minimal, if any, side effects in our study, since we are using a dose (40mg/day) which is lower than the 80mg/day used in several of the above mentioned studies. And, we feel there are no special concerns in the patient population included in our study (non-traumatic ICH) since conivaptan has already been safely used in TBI ICH patients.

An evaluation of the safety assessment parameters of each of the seven (7) subjects will be done by the PI and Co-I during the patient's care. Should events occur regarding the administration of conivaptan that raise safety concerns, the PI has the authority to withdraw the subject and/or halt the study pending further investigation.

Specific safety assessment parameters will include the following-

- **Neurologic tolerability:**
 1. Seizure frequency (15-20% of patients with ICH have seizures associated; EEGs will be used and measured; all treatments will be the same, using anti-seizure drugs).
 2. Total Na+ mEq received.
 3. ICP variability. In all patients for whom ICP is monitored, the hourly mean and median ICP will be compared. Further, patients will be graphed and the area-under-the-ICP-curve and above 10, 15, and 20 mmHg will be calculated and averaged to provide a more continuous comparison.
 4. ICP response to osmotic therapy. In patients receiving mannitol or 23.4% NaCl boluses, the average ICP reduction in the hour following administration will be compared.
 5. Development of central pontine demyelination, expansion of initial ICH, new ICH or stroke.

- **Cardiac tolerability:**
 1. Troponin values.
 2. Development of new arrhythmia during ICU stay.

- **Pulmonary tolerability:**
 1. Development of pulmonary edema as determined by chest X-ray.
 2. Average PO₂, FiO₂, A-a gradient.

- **Renal tolerability:**
 1. Change in renal function/urine output. RIFLE criteria will be used to assess for development of renal dysfunction (Appendix 1).
 2. Need for renal replacement therapy (RRT).

- **Infectious tolerability:**
 1. Compare rates of BSI, VAP/HAP, UTI, and sepsis.

- In-hospital mortality stratified by APACHE II, GCS, and ICH Score.

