8.1 Data Reviewed

- Demographics: Age, race, gender, and risk factors (hypertension, diabetes, illicit drug use, coronary artery disease, stroke, alcohol use).
- Clinical Grading Scores:
 - Outcome: mRS (Appendix 2) at baseline and discharge (if available). This can be performed by study team or as part of normal clinical practice.
 - ICH score at baseline (Appendix 5).
 - GCS score at baseline, 24 hrs from enrollment, 72 hrs from enrollment 7 day and discharge (if available) (Appendix 4).
 - APACHE II at baseline (Appendix 3).
- Duration of Neruo-ICU and hospital stay.
- Need for any of the following:
 - EVD/Bolt.
 - Hemi-craniectomy.
 - Central venous line/PICC/Arterial line.
 - RRT.
- Concomitant osmotherapy:
 - Hypertonic saline. The total mEq delivered and form of delivery (i.e. NS vs. 3% NaCl solution vs 23.4% NaCl solution.)
 - Mannitol. Number of doses and total grams received.
- Concomitant medications
- Imaging evaluation: CT scans will be dichotomized and ICH volume and CE volume will be compared over time. The individual summed and averaged volumes, net ICH volume and edema volumes will be compared. A board certified/eligible radiologist will calculate serially

the hemorrhage volume on CT during the study period. ICH volume will be serially assessed both by the $(Ax \times B \times C)/2$ method and by volumetric calculations using volumetric software. Serial assessments of edema will occur by measurements of the length and width of regional edema in the CT slice demonstrating the greatest amount of edema. Volumetric calculations using volumetric software will also be employed to evaluate for CE volume. Further, the same measurements one slice above and below will be performed to allow for a volumetric comparison. Completed CT scan measurements and calculations will be e-mailed to the research coordinator for data entry. In addition to the planned imaging and chemistry panels, any other imaging or basic laboratory work, deemed medically necessary for patient care outside the study, will be evaluated in the final analysis.

Clinical data collected from time of ICU admission to day 7:

- Vital signs (BP, HR, Temp)
- Daily weights and admission height
- ICP/ CPP values- when available/when a monitor is being used
- CVP values- when available
- Volumes for intake and output.
- Na⁺ values
- Cl⁻ values
- Cr values
- BUN values
- PO₂ values- when available
- PCO₂ values-when available
- A-a gradient- when available

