- Participation in another study for ICH or intraventricular hemorrhage.
- ICH related to infection, thrombolysis, subarachnoid hemorrhage, trauma or tumor.
- Presence of HIV or active fungal infection that is known based on information in the EMR.

- Continued use of digoxin or amlodipine (as recommended by the manufacturer due to CYP3A inhibition).
- Active hepatic failure as defined by AST >160 units/L and/or ALT >180 units/L, or total bilirubin levels greater than four times normal levels (>4.8mg/dL).
- Serum Na⁺ ≥ 145 mmol/L (admission labs or any time prior to recruitment/enrollment).
- Unable to receive conivaptan based on contraindications indicated by the manufacturer.
- Pregnant or lactating females.
- Not expected to survive within 48 hours of admission, or a presumed diagnosis of brain death.

5. Statistical Methods

5.1: Study Subjects and Analysis Sets

All enrolled patients will be included in a single analysis set and data will be summarized using frequencies and percentages.

5.2: General Methodology

This study is looking to preliminarily evaluate the safety, tolerability, and efficacy of conivaptan treatment. Unfortunately, it is not powered to provide robust statistical evaluation of safety and tolerability, nor to detect differences in efficacy between subjects. As such, all analysis will be descriptive in nature. Categorical variables will be summarized using counts and percentages. Continuous variables will be summarized using descriptive statistics: number of patients, mean, median, and full range, as appropriate.

Statistical analysis will consist of:

- Descriptive analysis of patient characteristics
- Frequency of relevant complications and medical interventions
- Changes in CE volume

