5.3 Evaluation of Objectives

Safety and tolerability will be assessed via the number of patients that experience abnormal seizure activity, show abnormal laboratory values, have increased infection rates, or exhibit an adverse events directly related to treatment with conivaptan. The change in CE volume will be reported as a measure of potential efficacy, and potential impacts on cost of care will be assessed by the length of stay in the ICU and the use of medical interventions to reduce CE volumes. Patient outcomes will be assessed using the mRS at discharge. Due to the small number of patients in this trial and absence of a control group, all evaluation will be descriptive only.

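### Item 3 of protocol 6.9 is called ICP variability, but no listed statistic directly measures within-patient variability; the threshold areas reflect swings only indirectly, mixed with level

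*Protocol*

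**What the plan says.** Protocol section 6.9 sets out the primary safety and tolerability assessments. Item 3 under neurologic tolerability reads "ICP variability. In all patients for whom ICP is monitored, the hourly mean and median ICP will be compared". It goes on to say that patients will be graphed and that "the area-under-the-ICP-curve and above 10, 15, and 20 mmHg will be calculated and averaged to provide a more continuous comparison". The item names no standard deviation, within-patient range, successive difference or count of excursions.

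Item 4 is a separate ICP measure. In patients given mannitol or 23.4% saline boluses, "the average ICP reduction in the hour following administration will be compared". It concerns response to osmotic therapy, not the variability of ICP over the monitored period.

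Protocol section 8.1 limits the data: "ICP/ CPP values- when available/when a monitor is being used". Section 6.8 leaves the choice of monitoring devices to the treating physicians.

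SAP section 5.2 gives one rule for all continuous variables: "Continuous variables will be summarized using descriptive statistics: number of patients, mean, median, and full range, as appropriate". SAP section 5.3 begins its list of safety measures with "Safety and tolerability will be assessed via the number of patients that experience abnormal seizure activity, show abnormal laboratory values, have increased infection rates" and ends it with adverse events directly related to conivaptan. ICP is not named there.

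**The concern.** The name of the parameter and its definition do not match. Variability is a question of spread within a patient over time. Mean, median and total area answer how high ICP was. Area above a threshold answers how much ICP was above that line, and swings enter it only when they cross the line.

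The question itself is reasonable here. The drug is given as boluses every 12 hours, section 6.7 includes acute aqueresis in the likely mechanism, and section 6.8 schedules CT partly to look for rebound edema. A reader of the results would expect an item with this name to say whether ICP was steady between doses. With the listed statistics, an unchanged mean could be reported under the heading of variability and be taken as evidence of stable ICP.

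**Working it through.** The plan states no figure for this item, so there is nothing to reproduce. The check computes the item's own statistics on artificial traces. The ICP values are assumptions, because the documents give no ICP data. Taken from protocol 6.9: hourly mean and median, area under the curve, and thresholds of 10, 15 and 20 mmHg. Assumed: 48 hours of monitoring, one value per minute, and either a flat trace at m or m + a·sin(2πt/P) with period P of 1 or 12 hours.

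**Formulas.** Total area = mean × 48. Area above c = average of max(ICP − c, 0) × 48. SD of a sinusoid = a/√2.

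**1. Swings inside one threshold band.** If ICP never crosses c, the area above c is either zero or (mean − c) × 48, so it carries no information beyond the mean and the monitored time. For m = 25 and a = 4, ICP runs from 21 to 29 and stays above 20:

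| Statistic | Flat 25 | 25 ± 4, P = 1 h |
|---|---|---|
| Every hourly mean and hourly median | 25 | 25 |
| Total area, 25 × 48 (mmHg·h) | 1200 | 1200 |
| Area above 10, 15 × 48 | 720 | 720 |
| Area above 15, 10 × 48 | 480 | 480 |
| Area above 20, 5 × 48 | 240 | 240 |
| Within-patient SD | 0 | 4/√2 = 2.83 |
| Within-patient range | 0 | about 8 |

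The same happens at low pressure. Flat 6 and 6 ± 3.5 (maximum 9.5, below 10) both give total area 6 × 48 = 288 and all three threshold areas 0, with SD 0 versus 3.5/√2 = 2.47.

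**2. Slow swings.** For 25 ± 4 with P = 12 h, the overall mean, the overall median and all four areas are those of flat 25, and the SD is 2.83. The hourly means now run from 21.2 to 28.8, so the swing is visible in the hourly series and on a graph. No planned statistic condenses it. The mean absolute hour-to-hour change, the average of |h(k+1) − h(k)| over the 47 successive pairs of hourly means, would be 1.26 mmHg against 0 for the flat trace.

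**3. Swings that cross a threshold.** Here the areas do respond. Flat 15 versus 15 ± 8 (P = 12 h) gives area above 15 of 0 versus (8/π) × 48 ≈ 122, and area above 20 of 0 versus about 27 mmHg·h. That single figure of 27 is not specific to swings: 27/48 ≈ 0.56, so a steady ICP of about 20.56 mmHg gives the same area above 20.

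**4. Normal hourly values (a second assumption).** Expected area per hour above c is (μ − c)·Φ((μ − c)/σ) + σ·φ((μ − c)/σ). At μ = 15:

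| Threshold | σ = 2 | σ = 8 |
|---|---|---|
| 10 | 5.00 | 6.30 |
| 15 | 0.80 | 3.19 |
| 20 | 0.004 | 1.295 |

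At a fixed mean the expected area rises strictly with σ. Under normality, then, the mean and one threshold area together determine the SD. The listed panel is not blind to all swings, but the spread would have to be inferred through a distributional assumption that the plan does not make.

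**The case against.** The strongest reply is that the panel as a whole carries a good deal about swings. A reader might infer from the mismatch that ICP swings go unmeasured altogether, or that every listed statistic is purely one of level. The documents do not support that. Steps 3 and 4 show threshold areas changing sharply at the same mean (0.004 versus 1.295 above 20 mmHg), and steady and swinging patients who agree on one area will usually differ on the mean or another area. Item 3 also plans a graph of each patient, which with so few patients shows hour-to-hour swings directly. This part of the reply stands, and it limits the point to the absence of a direct measure.

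The SAP's full range is a measure of spread, but it belongs to a generic summary that starts with the number of patients. It is not stated to be within-patient, and nothing ties it to ICP.

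A reader might also infer that conivaptan is expected to widen ICP swings. The documents do not say so. They report a prolonged reduction in ICP with the drug, and the rebound they describe as a known problem is attributed to mannitol.

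The reply that the matching traces are special is partly right: they stay inside one band, and identity on the hourly values needs swings within the hour. One of those bands, however, is all ICP above 20 mmHg, the protocol's highest threshold. Finally, renaming the item would by itself remove the mismatch. That is true, but it would leave the named question unanswered.

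**Conclusion.** The point holds in a limited form. Item 3 is called variability, and none of its statistics directly measures within-patient variability. The threshold areas reflect swings only indirectly and mixed with level, and not at all while ICP stays within one band. The graphs show slow swings without summarising them, and the SAP does not supply the missing statistic. The example of SD 0 versus 2.83 mmHg with every listed statistic equal rests on assumed traces. It shows that the gap can occur, not how often it would.

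The consequence is modest. This is one of many listed safety parameters in a descriptive, uncontrolled study of seven patients, and only those with a monitor contribute. No stated stopping rule uses it. It would be wrong to read it as undermining the safety evaluation as a whole.

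**What to change.** In protocol 6.9 item 3 and in the SAP, define two quantities with one value per monitored patient:

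- the within-patient SD (or range) of the individual recorded ICP readings, not only of hourly means;
- the mean absolute hour-to-hour change in ICP.

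Report these as ICP variability, with the number of monitored patients and the hours each contributes. Relabel the hourly mean, median and area measures ICP level/burden. Add ICP to the safety measures in SAP 5.3.

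The individual readings matter: in the within-hour example the hourly means are all 25, so both their SD and their hour-to-hour change are 0. The documents do not say how often ICP is recorded. If only one reading an hour is available, swings within the hour cannot be recovered, and the report should say so.

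The cost is two summary statistics from values already collected, with no extra procedures, visits or patients. The minimum alternative is to rename the item, so that a steady mean is not reported as steady ICP.
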